1 STUDY SYNOPSIS

Provide a structured synopsis containing all important information, preferably in tabular view:

Sponsor-Investigator	Prof.Dr.med. [name] MPH MHA, labormedizinisches zentrum [name], [name], email [contact]; [contact]; Mobile [contact]
Study Title:	Defining the role of a fertility bracelet for early recognition and monitoring of COVID- 19 in Liechtenstein (COVI-GAPP)
Short Title / Study ID:	A fertility tracker for recognition of COVID-19
Protocol Version and Date:	Version 1.1 (dated 06/04/2020)
Trial registration:	Intended registry: International Standard Randomised Controlled Trial Number (ISRCTN) registry
Study category and Rationale	Category A according to ClinO Art 20. The fertility tracker has a CE-mark, in the intended use, it is stated by means of the fertility tracker, "parameters are collected to improve the quality of the prediction and to provide general information on health and wellness". The fertility tracker employs non-invasive nightly monitoring of temperature, breath rate, pulse rate, and movements during sleep.
Clinical Phase:	Phase of development an algorithm for early recognition and monitoring of COVID- 19
Background and Rationale:	Nightly monitoring of temperature, breath rate, pulse rate, movement by means of the AVA bracelet originally intended for cycle tracking in women. Whereas temperature is a sign of inflammation, breath rate can be regarded in function of affected airways, heart rate variability can be regarded as a marker of stress. All these parameters are expected to be altered in COVID-19 infection. From the measurements, algorithms for early prediction of COVID-19 will be developed. Risk for participants is low (non-invasive monitoring and blood sampling)
	the expected benefit is large, as algorithms trained on the obtained data recordings are expected to recognize COVID-19 earlier than clinical symptoms. The latter would allow for earlier isolation and stratification as well as monitoring of COVID-19 affected patients preventing further spread and allowing for appropriate healthcare.
Objective(s):	Primary objective A.) To see whether the AVA bracelet is capable to reliably identify persons with COVID19 infection early, before they get clinically. This would allow for early isolation and testing of contact persons, thereby preventing extensive spreading of the Virus. When reversing the process of lockdown of social and economic systems or during a so called second wave of the COVID-19 pandemic, the AVA bracelet could serve as a sensitive tool to observe relapsing infection rates.
	Secondary objective
	a.) To see whether the AVA bracelet would serve to recognize severe cases early allowing for risk stratification, early treatment and allocation of adequate care to patients with COVID19.
	b.) To obtain a seroprevalence of COVID19 affected cases in the population of Liechtenstein.
Outcome(s):	Occurrence of COVID-19 infection, Severity of COVID-19 infection.
Study design:	Observational population-based cohort study employing a CE-marked medical device.
Inclusion / Exclusion criteria:	Inclusion criteria: participant of the GAPP study. Exclusion criteria: Inability to provide informed consent.

Measurements and	Serological status for SARS-CoV2-antibodies will be determined at the beginning and the end of the study.			
procedures:	The participants will be asked to answer a questionnaire about recent infections at study entry, undergo baseline serological testing. Study participants will be monitored overnight with the employed fertility tracker. We will collect information about clinically documented infections in all participants during follow-up, and provide serology at the end of the study.			
	The study and participant recruitment will be performed within the study organization of the GAPP study, an ongoing prospective follow-up study. Baseline characteristics and other clinical information will be used from the GAPP study database.			
Study Product / Intervention:	The fertility tracker automatically saves physiological information every 10 seconds throughout the night, requiring at least 4 hours of relatively uninterrupted sleep each night to stabilize parameter measurements. The wrist-worn bracelet acts as a data logger, recording and storing user's physiological sensors signals as raw datasets throughout the night. Currently, the user synchronizes the bracelet to the mobile phone application the following morning. It is planned that participants wear the fertility tracker overnight during the study period.			
Control Intervention (if applicable):	Not applicable			
Number of Participants with Rationale:	Participants of the ongoing population based GAPP cohort study conducted in Liechtenstein will be included (n=2170; study approved by KEK ZH StvNr. 66/09). These will receive the AVA bracelet for free. We eventually might attain a sample size of 5000 participant by onboarding additional participants. For this second phase, we will seek separate ethical approval.			
Study Duration:	The course of the pandemic can currently not be predicted and is critical for the duration of the study. WE anticipate a duration of nearly 3 years.			
Study Schedule:	Participants should be included as fast as possible, in order to catch as many endpoints during the COVID-19 pandemic.			
	Planned 12/04/2020 of First-Participant-In			
	Planned 31/12/2021 of Last-Participant-Out			
	Depending on the course of the pandemic, the study can be terminated earlier.			
Investigator(s):	[name].med. [name], McMaster University, Hamilton ([contact]), Dr.med. [name], Private University Liechtenstein, Triesen ([contact]), [name], Universität Basel ([contact]), [name] MSc, Private University Liechtenstein ([contact]), Dr.[name] PhD, Chief medical Officer AVA for women ([contact])			
Study Centre(s):	Single-centre study. GAPP-Studie c/o labormedizinisches zentrum [name], [name]			
Statistical Considerations:	Prediction of the development of COVID-19 infection will be modeled on the base of nightly monitoring of temperature, breath rate, pulse rate and movements by means of machine learning methods. Algorithms will be trained by comparing monitoring data of COVID-19 diseased and non-diseased individuals by a big data approach employing machine learning. The project partner AVA for women has already used such an approach to predict fertile days in women with a higher than 90% accuracy. The seroprevalence of COVID-19 will be presented as count (percentage) and we			
	will standardize these numbers to the general population of the Principality of Liechtenstein. The sample size is given by the sample size included in the GAPP study.			
GCP Statement:	This study will be conducted in compliance with the protocol, the current version of the Declaration of Helsinki, ISO EN 14155 as well as all national legal and regulatory requirements.			

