4.3 Study procedures

The study starts as soon as ethical approval is obtained, preferably in calender week 15 2020. The rapid study start is intended in order to capture as many COVID-19 cases as possible. The study will be ongoing until the COVID-19 pandemic is eradicated, a vaccine or curative therapy has become available, or if the Investigators come to the decision to terminate the study. Due to the unclear course of the pandemic, it is not possible to provide an exact date of study duration. We anticipate that the study should be terminated on 31st December 2021 the latest.

First, study participants will be contacted by mail with the study information and the informed onsent sheet. After providing informed consent (in case of questions, the study staff can be contacted for questions at the contact information already known to the study participants) the study participants, baseline clinical information is provided in a study questionnaire. The study participants will then obtain an AVA bracelet, either by post or in the study center. Informed consent will be discussed personally on the occasion of a personal contact due to provision of the AVA bracelet or presentation for blood sampling.

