6.5 Amendments

Substantial changes to the study setup and study organization, the protocol and relevant study documents are submitted to the Ethics Committee for approval before implementation. Under emergency circumstances, deviations from the protocol to protect the rights, safety and well-being of human subjects may proceed without prior approval of the Ethics Committee. Such deviations shall be documented and reported to the Ethics Committee as soon as possible.

Substantial amendments are changes that affect the safety, health, rights and obligations of participants, changes in the protocol that affect study objective(s) or central research topic, changes of study site(s) or of study leader and sponsor (ClinO, Art. 29).

A list of substantial changes is also available on www.swissethics.ch.

A list of all non-substantial amendements will be submitted once a year to the competent EC together with the ASR.

6.7 (Premature) termination of study

The Sponsor-Investigator may terminate the study prematurely before 31st December 2021,

- When the COVID-19 pandemic is eradicated,
- A vaccine or curative therapy has become available

- Insufficient compliance of the study participants to the study protocol
- Due to ethical concerns,
- Due to insufficient participant recruitment,
- When the safety of the participants is doubtful or at risk (e.g. when the benefit-risk assessment is no longer positive),
- Alterations in accepted clinical practice occure that make the continuation of the study unwise
- Early evidence of harm or benefit of the observations with the AVA bracelet

Upon regular study termination, the Ethics Committee is notified via BASEC within 90 days (ClinO, Art. 38).

Upon premature study termination or study interruption, the Ethics Committee is notified via BASEC within 15 days (ClinO, Art. 38).

The www.swissethics.ch template concerning the notification of completion, discontinuation or interruption of the clinical trial is used for this purpose.

Health-related data at the end of the study are introduced into the GAPP study database.

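### The stated duration does not fit the planned dates, sections 4.3 and 6.7 disagree on whether a vaccine ends the study, and a final serology sample taken after vaccination could be counted as infection

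*Protocol*

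**What the plan says.** **Duration.** The Study Duration row of the synopsis reads "WE anticipate a duration of nearly 3 years". The Study Schedule row below it gives "Planned 12/04/2020 of First-Participant-In" and "Planned 31/12/2021 of Last-Participant-Out", and adds that the study may stop sooner. Section 4.3 sets the start ("The study starts as soon as ethical approval is obtained, preferably in calender week 15 2020") and an outer limit ("We anticipate that the study should be terminated on 31st December 2021 the latest"). Section 6.7 calls an end before that same date premature.

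**Vaccine.** Section 4.3: "The study will be ongoing until the COVID-19 pandemic is eradicated, a vaccine or curative therapy has become available". The sentence goes on to allow the investigators to decide to stop. Section 6.7: "The Sponsor-Investigator may terminate the study prematurely before 31st December 2021", followed by a list of grounds that includes "A vaccine or curative therapy has become available".

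**Serology.** Section 3.2 defines the primary endpoint as COVID-19 infection, established clinically, by antibody testing, by RT-PCR, or by a combination. Section 3.1 makes seroprevalence a secondary objective. Sections 3.4 and 4.3 and the synopsis place the last antibody sample at study end, with no calendar date. The synopsis also plans a baseline sample. Section 4.3 describes surveys about every 14 days on health status, and symptom reporting during the study. Neither description mentions vaccination.

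**The concern.** There are two separate inconsistencies about when the study ends. The first is a stated length that the stated dates cannot produce. The second is whether the arrival of a vaccine closes the study or only gives the sponsor-investigator the option to close it.

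The second bears on the endpoint. The last antibody sample has no date of its own and moves with the study end. The protocol twice names a vaccine as a foreseeable event within the study's life, yet section 3.2 lets antibodies establish infection without separating those caused by infection from those caused by vaccination. At stake are the labels on which the algorithm is trained and judged (infected or not) and the seroprevalence estimate. Vaccination dates that are not collected during follow-up are hard to recover afterwards, and a later analysis plan cannot exclude post-vaccination samples that it has no means to identify.

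**Working it through.** **1. Duration from the planned dates**

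Inputs: first participant in 12 April 2020 and last participant out 31 December 2021 (synopsis, Study Schedule).

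- 12 April to 31 December 2020: 18 + 31 + 30 + 31 + 31 + 30 + 31 + 30 + 31 = 263 days.
- 31 December 2020 to 31 December 2021: 365 days.
- Total: 263 + 365 = 628 days.
- In months: 628 / 30.4375 = 20.6.
- In years: 628 / 365.25 = 1.72.

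**2. Can any reading of the dates reproduce the stated duration?**

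The protocol does not define nearly 3 years. I assume 33 to 36 months.

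| Start date used | Days to 31 Dec 2021 | Months |
|---|---|---|
| 12 April 2020 (synopsis) | 628 | 20.6 |
| 6 April 2020 (protocol date, first day of calendar week 15) | 634 | 20.8 |
| 4 December 2020 (12/04 read as month/day) | 392 | 12.9 |

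None comes near 33 months. Against 12 April 2020 the excess is 33 - 20.6 = 12.4 months to 36 - 20.6 = 15.4 months. Counting 33 to 36 months from that start puts the end between about 11 January and 12 April 2023, after the limit in section 4.3. Uncertainty about the pandemic does not close the gap, because the text provides only for an earlier end.

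**3. The vaccine rule, side by side**

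- Section 4.3: the study continues until one of several events, of which vaccine availability is one. Read plainly, availability ends it.
- Section 6.7: the same event is one of several grounds on which the sponsor-investigator may end it early. Continuing to 31 December 2021 is allowed.
- The investigator discretion added in section 4.3 is discretion to stop. It does not authorise continuing past a vaccine, so it does not bring the two sections into agreement.

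**4. What follows for the final sample**

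- Under section 6.7, the study can run on to 31 December 2021 with a vaccine in use, and the final sample is drawn at that end.
- Under section 4.3, the final sample comes after a vaccine has become available. What counts as available is not defined, so some draws could still follow a dose, although the window is shorter.
- A participant negative at baseline and positive at the end could have been infected or vaccinated. Baseline serology does not separate the two.
- A vaccination date would help to separate them. Section 4.3 and Appendix 1 name no item that collects it.

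This chain needs one condition that the protocol leaves open: the assay must react to vaccine-induced antibodies. The antibody target is not stated.

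**The case against.** The strongest reply is that the first inconsistency is editorial. The end date is the same in the synopsis, section 4.3 and section 6.7, and only one sentence disagrees. Section 5.1 takes the sample size from the existing cohort, and no event count, person-time or power figure uses the duration. This stands. A reader might infer that the error inflates planned exposure or causes the vaccination problem; the documents support neither. The vaccination problem comes from the undated final sample and the endpoint definition, and it is larger under section 6.7 than under section 4.3.

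A second reply is that sections 4.3 and 6.7 list similar triggers, both leave some discretion, and need only aligned wording. They are close, but one lets the study continue after a vaccine and the other, read plainly, does not.

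A third reply is that handling of vaccine antibodies may sit in an analysis plan that is not shown, and that section 3.2 records how each infection was diagnosed, so serology-only cases can be set apart. That is partly right: RT-PCR and clinical diagnoses are unaffected, and serology-only positives can be listed. But listing them does not show which were vaccinated. The endpoint definition and the data collected are set in this protocol, and an analysis plan cannot use dates that were never asked for.

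A reader might also try to size the damage by setting an assumed vaccinated share of the 2170 against the incidence in section 4.2. That comparison is unreliable. The incidence counts confirmed cases in the first weeks of the outbreak rather than infections over some 20 months, full enrolment and a final sample from everyone would have to be assumed, and the assay's response to vaccination is unknown.

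**Conclusion.** The concern holds in a limited form. Two contradictions are certain from the current text: a stated duration 12.4 to 15.4 months longer than the planned dates allow (taking nearly 3 years as 33 to 36 months), and a vaccine rule that reads as ending the study in section 4.3 but as optional in section 6.7.

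The consequence for the endpoint is conditional. It requires that some final samples follow vaccination and that the assay detects vaccine-induced antibodies. If both hold, vaccinated participants would be counted as infected in the primary endpoint and in seroprevalence, and the described data collection would not identify them. The number cannot be estimated from the protocol; if the assay does not respond to vaccination, it could be near zero. It would go too far to say that the primary endpoint as a whole is lost, because RT-PCR and clinical diagnoses and pre-vaccination serology keep their meaning.

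This should be corrected while follow-up data can still be collected.

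**What to change.** 1. In the synopsis, replace the duration with about 20.6 months, ending on 31 December 2021 at the latest.
2. Reconcile sections 4.3 and 6.7 on what vaccine availability means for the study. Which rule applies is for the sponsor to decide; the two sections must say the same thing.
3. Add vaccination status and date to the periodic questionnaire (about every 14 days) and to the final visit.
4. In section 3.2, state that a positive antibody result from a sample taken after vaccination does not by itself establish infection. Such a result is non-evaluable for infection and for seroprevalence unless the assay separates infection from vaccination. RT-PCR or clinical diagnoses and pre-vaccination serology continue to count. Non-evaluable must not be read as uninfected, since some of these participants may have been infected.

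The cost is wording, one questionnaire item, and the loss of some final samples for the infection and seroprevalence analyses.

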3.2 Primary and secondary endpoints

Primary endpoint is the occurrence of COVID-19 infection, as assessed by clinical signs, serology and/or RT-PCR testing Date of occurrence, clinical symptoms and laboratory results, how infection was diagnosed is collected to describe the primary endpoint. The endpoints will be collected by periodic reports obtained on questioning the study participants. Participants and the

treating healthcare institutions will be contacted to obtain respective information.

As a secondary endpoint severity of COVID-19 infection will be assessed. Participants and the treating healthcare institutions will be contacted to obtain respective information. The following parameters will be collected: Hospitalization needed within 30 days of COVID-19 diagnosis (including timing)? ICU admission within 30 days of COVID-19 diagnosis (including timing)? Use of mechanical ventilation within 30 days of COVID-19 diagnosis (including timing)? Participant reported health status after COVID-19 diagnosis (including timing)? COVID-19 related mortality? Quantiative RT-PCR results (viral loads) and quantitative Immunoassay results of COVID-19 specific laboratory markers? Results of other respiratory pathogens in COVID-19 negative participants available? Further healthcare contact of patients tested negative for COVID-19?

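### The stated seroprevalence estimate carries no correction for assay error, and the primary endpoint wording lets a positive antibody test alone count as an infection

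*Protocol*

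**What the plan says.** Seroprevalence is secondary objective b (section 3.1). The synopsis, under Statistical Considerations, gives its analysis: "The seroprevalence of COVID-19 will be presented as count (percentage", after which the investigators "will standardize these numbers to the general population of the Principality of Liechtenstein". No assay, sensitivity, specificity or confirmatory test is named.

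Section 3.2 reads: "Primary endpoint is the occurrence of COVID-19 infection, as assessed by clinical signs, serology and/or RT-PCR testing". It adds that "how infection was diagnosed is collected to describe the primary endpoint", but attaches no rule on which route suffices or needs confirming. The synopsis states that the algorithm is trained by comparing diseased with non-diseased participants, so the case definition supplies the labels.

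On timing, the synopsis says: "Serological status for SARS-CoV2-antibodies will be determined at the beginning and the end of the study". Appendix 1 also lists sampling at time 0, while sections 3.4 and 4.3 mention only the final draw.

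On study end, section 4.3 says: "The study will be ongoing until the COVID-19 pandemic is eradicated, a vaccine or curative therapy has become available", or until the investigators decide to stop, with 31 December 2021 as the latest date. Section 6.7 lists an available vaccine among grounds on which "The Sponsor-Investigator may terminate the study prematurely before 31st December 2021". Nothing in the protocol records vaccination.

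**The concern.** When few people have been infected, even a specific antibody test yields false positives in numbers similar to or above the true ones. A percentage that takes the test at face value then overstates how many were infected, and standardising it turns that error into a national figure.

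The same results can enter the primary endpoint. A participant labelled as a case on a false-positive antibody test has no infection signal in the bracelet data. Training and testing on such labels tends to lower the algorithm's apparent sensitivity and blurs the patterns it is meant to learn.

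A second, conditional source of error is vaccination. If the study continued after a vaccine became available and the assay detected vaccine antibodies, the final draw could count vaccinated participants as infected.

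**Working it through.** The protocol gives no expected seroprevalence, assay performance or precision target, so there is no figure of its own to reproduce.

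**Inputs from the protocol.** N = 2170 (section 5.1). Reported incidence 1582 per million = 0.158% (section 4.2), a count of reported cases from the first weeks after 2 March 2020.

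**Assumptions.** Sensitivity (Se) 90%; specificity (Sp) 98%, 99%, 99.5% and 99.8%; true prevalence p of 1%, 5% and 10% beside 0.158%; all 2170 tested.

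**Formulas.**
- True positives = N × p × Se
- False positives = N × (1 − p) × (1 − Sp)
- Apparent prevalence = Se × p + (1 − Sp) × (1 − p)
- Share of positives that are true = true positives / all positives

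Example, p = 0.158% and Sp = 99%: true positives 2170 × 0.001582 × 0.90 = 3.1; false positives 2170 × 0.998418 × 0.01 = 21.7; share true 3.1/24.8 = 12.5%.

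In each cell below, values are for Sp 98% / 99% / 99.5% / 99.8%.

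| True prevalence | True positives | False positives | Apparent prevalence (%) | Share of positives true (%) |
|---|---|---|---|---|
| 0.158% | 3.1 | 43.3 / 21.7 / 10.8 / 4.3 | 2.14 / 1.14 / 0.64 / 0.34 | 6.7 / 12.5 / 22.2 / 41.6 |
| 1% | 19.5 | 43.0 / 21.5 / 10.7 / 4.3 | 2.88 / 1.89 / 1.40 / 1.10 | 31.2 / 47.6 / 64.5 / 82.0 |
| 5% | 97.7 | 41.2 / 20.6 / 10.3 / 4.1 | 6.40 / 5.45 / 4.98 / 4.69 | 70.3 / 82.6 / 90.5 / 95.9 |
| 10% | 195.3 | 39.1 / 19.5 / 9.8 / 3.9 | 10.80 / 9.90 / 9.45 / 9.18 | 83.3 / 90.9 / 95.2 / 98.0 |

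**Direction of bias.** Setting apparent equal to true prevalence gives p = (1 − Sp) / ((1 − Se) + (1 − Sp)). Below this point the uncorrected figure is too high; above it, missed infections outweigh false positives and it is too low.
- Sp 98%: 0.02/0.12 = 16.7%
- Sp 99%: 0.01/0.11 = 9.1%
- Sp 99.5%: 0.005/0.105 = 4.8%
- Sp 99.8%: 0.002/0.102 = 2.0%

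**Standardisation.** With population weights w summing to 1 and the same Se and Sp in every stratum, the weighted apparent prevalence is Se × p* + (1 − Sp) × (1 − p*), where p* is the standardised true prevalence. The assay error passes through unchanged.

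**Correction.** Rogan-Gladen: p = (apparent + Sp − 1) / (Se + Sp − 1). At Se 90%, Sp 99% and apparent 1.89%, this is (0.0189 − 0.01)/0.89 = 1.0%, the true value assumed.

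**Vaccine illustration.** Assume true prevalence 5%, Se 90%, Sp 99%, and that 95% of vaccinated uninfected participants test positive. With coverage v, apparent prevalence = 0.05 × 0.90 + 0.95 × (0.95v + 0.01(1 − v)). This gives 14.4% at v = 10%, 32.2% at 30% and 59.0% at 60%, against 5.45% with no vaccination.

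**The case against.** Several stronger readings are tempting, and the protocol does not support them.

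- **That the percentage is raw.** It is to be standardised to the population. That leaves assay error in place, but the figure is not a plain crude percentage.
- **That the bias is always upward.** It is not; the crossover values show where it reverses.
- **That 0.158% describes what the study will find.** It is early reported incidence, whereas the final draw may come as late as December 2021. False positives matter much less above about 5% prevalence.
- **That every positive antibody test is by rule an infection.** The wording in section 3.2 is ambiguous: it permits that reading without prescribing it. The route of diagnosis and quantitative immunoassay results are collected, and baseline serology can reveal participants who test positive at both draws.
- **That reported intervals ignore assay uncertainty.** The protocol states no intervals for seroprevalence.
- **That vaccine antibodies will be counted as infection.** Section 4.3 ties the end of the study to a vaccine, and the discretion in section 6.7 can be read as the authority to act on that. Harm needs continuation, vaccination before the final draw and an assay that detects vaccine antibodies. No antigen is named.

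It is also fair to say that a correction for sensitivity and specificity could sit in a statistical analysis plan that is not at hand. Its absence alone would be no finding. What stands is what the protocol does state: an estimator without an assay-error term, and a primary case definition that admits serology alone with no confirmation rule. The latter is the firmer part.

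**Conclusion.** The concern holds in a bounded form. Followed as written, the protocol can report a seroprevalence distorted by assay error and can admit false-positive antibody results into the primary endpoint and the algorithm's labels.

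The size depends on prevalence and on an assay the protocol does not describe. Under the stated assumptions, false positives outnumber true ones at 0.158% across the whole specificity range. At 1% the balance runs from mostly false (98%) to mostly true (99.8%), and at 5% true positives predominate throughout. The low-prevalence setting is most relevant to the baseline draw, since first inclusion was planned for 12 April 2020.

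The vaccine part is conditional. What is certain is that sections 4.3 and 6.7 do not say the same thing and must be reconciled. The whole is a worthwhile, inexpensive improvement rather than a fatal flaw; the seroprevalence part touches a secondary objective only.

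**What to change.** 1. **Seroprevalence.** Beside the count, and before standardising, report an estimate corrected for assay sensitivity and specificity (Rogan-Gladen or a Bayesian equivalent), with an interval that carries the uncertainty of the assay's validation data.
2. **Primary endpoint.** Use the recorded diagnosis route to hold serology-only cases (no positive RT-PCR) as a separate category. Use baseline serology to identify participants already positive at entry. Repeat the algorithm analysis without serology-only cases as a sensitivity analysis, noting that this also drops true asymptomatic infections, because RT-PCR is prompted by symptoms.
3. **Vaccination.** Reconcile sections 4.3 and 6.7. If the study can continue once a vaccine is available, add vaccination date to the periodic questionnaire, and do not count antibody positivity first seen after vaccination as infection on its own.

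The cost is one questionnaire item, some analysis work and less precise estimates. At Se 90% and Sp 99%, the correction alone multiplies the sampling standard error by 1/0.89 = 1.12, before validation uncertainty is added.
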